
11. MEASUREMENT OF EFFECT

11.1 Antitumor Effect – Solid Tumors

For the purposes of this study, participants should be re-evaluated for response every 6 weeks for the first 6 cycles of therapy. Following completion of 6 cycles, imaging may be performed every 12 weeks at the discretion of the treating investigator. In addition to a baseline scan, confirmatory scans should also be obtained not less than 4 weeks following initial documentation of objective response. Participants who discontinue treatment prior to documented disease progression should continue to be followed for RECIST response evaluation until progression.

Response and progression will be evaluated in this study using the new international criteria proposed by the Response Evaluation Criteria in Solid Tumors (RECIST) guideline (version 1.1) [*Eur J Ca* 45:228-247, 2009]. Changes in the largest diameter (unidimensional measurement) of the tumor lesions and the shortest diameter in the case of malignant lymph nodes are used in the RECIST criteria.

11.1.1 Definitions

Evaluable for Target Disease response. Only those participants who have measurable disease present at baseline, have received at least one cycle of therapy, and have had their disease re-evaluated will be considered evaluable for target disease response. These participants will have their response classified according to the definitions stated below. (Note: Participants who exhibit objective disease progression prior to the end of cycle 1 will also be considered evaluable.)

Evaluable Non-Target Disease Response. Participants who have lesions present at baseline that are evaluable but do not meet the definitions of measurable disease, have received at least one cycle of therapy, and have had their disease re-evaluated will be considered evaluable for non-target disease. The response assessment is based on the presence, absence, or unequivocal progression of the lesions.

Unevaluable patients will be included in the analysis of response as non-responders assuming they were eligible and received study drug.

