5. TREATMENT PLAN

5.1 Treatment Regimen

Nivolumab will be administered once every 2 weeks, on cycle days 1, 15, and 29. Ipilimumab will be administered once every 6 weeks, on cycle day 1. A treatment cycle is defined as 6 weeks or 42 days. Treatment will be administered on an outpatient basis. Reported adverse events and potential risks are described in **Section 7**. Appropriate dose modifications are described in **Section 6**.

Table 3: Regimen Description					
Agent	Premedications	Dose^A	Route^B	Schedule	Cycle Length
Ipilimumab	None	1 mg/kg	IV over 60 minutes (\pm 5 minute infusion window)	Day 1	42 days (6 weeks)
Nivolumab	None	3 mg/kg	IV over 60 minutes (\pm 5 minute infusion window)	Days 1, 15, 29	

A. Calculation of body surface area (BSA) should be performed per institutional standards of practice. Re-calculation of dosage for fluctuations in body weight should be made in accordance with institutional guidelines.
 
B. On days where both nivolumab and ipilimumab will be administered, nivolumab should be administered first. The ipilimumab infusion will start at least 30 minutes after completion of the nivolumab infusion.
					

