5.6 Duration of Follow Up

Participants will be followed for a minimum of 90 days following their last dose of ipilimumab and 100 days following their last dose of nivolumab for serious adverse event (SAE) reporting. Participants removed from protocol therapy for unacceptable adverse event(s) will be followed at minimum until resolution or stabilization of the adverse event. Participants who are removed before documented disease progression should be followed for RECIST response criteria until disease progression or death. Following documentation of disease progression, participants will continue to be followed for a maximum of 3 years or until death for survival status only.

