13.1.2 Sample Size Considerations

The primary comparison will include all eligible and treated patients, of whom 80 will be accrued. Whereas traditional chemotherapy confers a response rate (CR + PR) of roughly 30%, the goal of this trial is to target a response rate of 44%, which will be taken as evidence of activity of combination therapy with ipilimumab and nivolumab. We will employ a Simon two stage design for this trial. In the first stage, a total of 43 eligible and treated patients will be enrolled. Accrual will proceed to the second stage if at least 15 patients achieve a CR or PR among those first 43 patients. In the second stage, an additional 37 patients will be enrolled. If at least 29 responses are observed among all 80 patients enrolled, then the combination of ipilimumab and nivolumab will be deemed worthy of additional study. This trial has 88% power against the null hypothesis while testing at the one-sided level of 0.109, and the probability that the study stops early under the null is 0.71.

We note that per RECIST 1.1, these responses must be confirmed with a second scan after the

initial response is determined. We also note that patients who are deemed unevaluable for response will not be replaced, and will be included as non-responders in the assessment of the best objective response rate.

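### Read literally, 11.1.1 scores a confirmed responder who stopped before receiving one cycle as a non-responder, in conflict with 11.1.3.4 and the response count in 13.1.2

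*Combined protocol and SAP*

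**What the plan says.** Section 11.1.1 states that only patients with measurable disease at baseline who "have received at least one cycle of therapy, and have had their disease re-evaluated will be considered evaluable for target disease response", and that these patients have their response classified. It makes one exception: "Participants who exhibit objective disease progression prior to the end of cycle 1 will also be considered evaluable". It closes with "Unevaluable patients will be included in the analysis of response as non-responders assuming they were eligible and received study drug". Section 13.1.2 repeats the rule for the primary endpoint: patients unevaluable for response are not replaced and "will be included as non-responders in the assessment of the best objective response rate".

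On exposure, section 5.1 says "A treatment cycle is defined as 6 weeks or 42 days", with nivolumab on days 1, 15 and 29 and ipilimumab on day 1. Section 6.2 lets cycle days keep counting when doses are held for toxicity.

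Three other places bear on the same patient and set no minimum exposure:

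- Section 5.6: "Participants who are removed before documented disease progression should be followed for RECIST response criteria until disease progression or death". Section 11.1 and the study calendar (Table 16) say the same for patients who stop treatment early.
- Section 11.1.3.4 takes the best response recorded from the start of treatment until progression.
- Section 13.1.2 bases the go/no-go counts (15 of 43, then 29 of 80) on patients who achieve a CR or PR among all eligible and treated patients.

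**The concern.** Take an eligible patient who receives the day 1 infusions, is permanently taken off drug before day 15 under one of the toxicity tables in section 6.1, continues scans as the protocol requires, and reaches a confirmed PR. Under 11.1.3.4 the best overall response is PR. Under 11.1.1 the patient has not received one cycle, is unevaluable, and counts as a non-responder. Two analysts following different sections would report different primary counts from the same scans.

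The situation is foreseeable. Section 6.1 requires permanent discontinuation for several toxicities that can occur within six weeks, and section 6.3 allows no dose reductions. The decision rules are integer cut-offs, so one response can separate 14 from 15 of 43, or 28 from 29 of 80. A responder recorded as a non-responder would also sit on the wrong side of the responder comparison in the correlative work, although section 13.1.3 treats subset analyses, including correlatives, as exploratory.

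A second gap is that receipt of one cycle is not defined. A patient with doses on days 1, 15 and 29 who stops on day 35 has arguably received a cycle. A patient dosed on day 1 with days 15 and 29 held may or may not have, depending on whether doses or elapsed days are counted.

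**Working it through.** **Inputs.** From section 13.1.2: null rate 0.30, target rate 0.44, 43 patients in stage 1, continue if at least 15 respond, 37 more in stage 2, success if at least 29 of 80 respond. Assumed, because the documents give no figure: f, the share of true responders who stop before receiving one cycle and are scored as non-responders.

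**Step 1: reproduce the stated design.** With X1 ~ Bin(43, p) and X2 ~ Bin(37, p):

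- P(stop at stage 1) = P(X1 ≤ 14)
- P(success) = Σ over x = 15..43 of P(X1 = x) · P(X2 ≥ 29 − x)

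At p = 0.30 these give 0.708 and 0.109. At p = 0.44 they give 0.086 and 0.884. The plan states 0.71, 0.109 and 88% power, so the design reproduces.

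**Step 2: effect of one miscounted responder.** The denominator is all eligible and treated patients, evaluable or not. Each such responder lowers the observed rate by 1/80 = 1.25 percentage points at the end, or 1/43 = 2.3 points at stage 1.

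**Step 3: effect of the early-progression exception.** A patient who progresses in cycle 1 is a non-responder if evaluable and a non-responder if unevaluable, and is in the denominator both times. The exception changes the response rate by exactly zero.

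**Step 4: range for f.** The counted rate is p(1 − f). Putting 0.44(1 − f) and 0.30(1 − f) into the Step 1 formulas, with expected responders lost = 80 × 0.44 × f out of 80 × 0.44 = 35.2:

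| f (assumed) | Counted rate at true 44% | Responders lost of 35.2 | Stop at stage 1, true 44% | Power | Type I error, true 30% |
|---|---|---|---|---|---|
| 0 | 44.0% | 0 | 8.6% | 88.4% | 0.109 |
| 2.5% | 42.9% | 0.9 | 11.1% | 84.6% | 0.085 |
| 5% | 41.8% | 1.8 | 14.1% | 80.1% | 0.064 |
| 10% | 39.6% | 3.5 | 21.7% | 68.6% | 0.034 |

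**Step 5: after the fix.** If these responses are counted, f = 0 and the first row applies. N, cut-offs and stated operating characteristics are unchanged.

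**The case against.** The strongest reply is that this is an unreconciled definition and not a settled rule. Sections 11.1, 11.1.3.4 and 13.1.2 all support counting the response, and a sensible analyst would do so. That is a fair reading of intent, but 11.1.1 says only patients meeting its conditions are evaluable, and 13.1.2 itself repeats that unevaluable patients are non-responders. The text that would settle the matter points the wrong way.

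The magnitude is also open to challenge. Nothing in the documents supports any particular f, and the 10% row should not be read as a forecast. The 44% target appears in the same section as the non-responder rule, so it may already describe the rate as counted; in that case there is no power loss against the design. The direction is conservative, since the rule cannot inflate the response rate. All of this stands, and it limits the size of the point.

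A reader might infer from the early-progression exception that the rule is biased because early progression counts while early response does not. Step 3 shows that it adds no bias. At most it shows that exposure of less than one cycle was considered for progression and not for response. A reader might also infer that everyone who stops during cycle 1 is affected. The text does not support that, because a patient given all the doses of the cycle has arguably received it.

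Finally, counting every confirmed response whatever the exposure would go too far. Scans continue until progression or death, and neither 11.1.3.4 nor 13.1.1 closes response assessment when another anticancer therapy starts. Without a limit, a response to later therapy after one study dose would count as a trial success. This objection stands and shapes the fix.

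**Conclusion.** The point holds as a conflict within the protocol over the primary count. The literal wording of 11.1.1 scores a confirmed responder with less than one cycle as a failure, against 11.1.3.4 and the count of responders in 13.1.2, and the exposure threshold is undefined. Any error is downward, at 1.25 points per patient at the end and 2.3 points at stage 1, and it is zero if no such responder occurs. The risk is a false negative or an unwarranted stage 1 stop; type I error falls rather than rises. The power losses in the table depend on an assumed f and on taking 44% as the true rate before this rule. The documents do not support a claim that the primary response rate will be biased, only that it would be if such a patient arises and 11.1.1 is applied as written.

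**What to change.** In 11.1.1:

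1. Replace the one-cycle condition with receipt of at least one dose of study drug.
2. State that any confirmed CR or PR in an eligible, treated patient, first documented before progression and before any subsequent anticancer therapy, counts as a response whatever the number of doses received.
3. Limit the unevaluable category, still counted as non-response, to patients without an adequate post-baseline assessment.

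Refer to the same definition in 13.1.2, and make the change before the stage 1 count.

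The cost is a few sentences. The scans are already required by 5.6, 11.1 and Table 16, and N and the cut-offs stay as they are. The one added requirement is that the start date of subsequent anticancer therapy be available for the response count.

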11.1.2 Disease Parameters

Measurable disease. Measurable lesions are defined as those that can be accurately measured in at least one dimension (longest diameter to be recorded) as ≥ 20 mm by chest x-ray or ≥ 10 mm with CT scan, MRI, or calipers by clinical exam. All tumor measurements must be recorded in millimeters (or decimal fractions of centimeters).

Note: Tumor lesions that are situated in a previously irradiated area are not considered measurable unless there has been demonstrated growth in the lesion.

Malignant lymph nodes. To be considered pathologically enlarged and measurable, a lymph node must be ≥ 15 mm in short axis when assessed by CT scan (CT scan slice

thickness recommended to be no greater than 5 mm). At baseline and in follow-up, only the short axis will be measured and followed.

Non-measurable disease. All other lesions (or sites of disease), including small lesions (longest diameter <10 mm or pathological lymph nodes with ≥ 10 to < 15 mm short axis), are considered non-measurable disease. Bone lesions, leptomeningeal disease, ascites, pleural/pericardial effusions, lymphangitis cutis/pulmonitis, inflammatory breast disease, abdominal masses (not followed by CT or MRI), and cystic lesions are all considered non-measurable.

Note: Cystic lesions that meet the criteria for radiographically defined simple cysts should not be considered as malignant lesions (neither measurable nor non-measurable) since they are, by definition, simple cysts.

‘Cystic lesions’ thought to represent cystic metastases can be considered as measurable lesions, if they meet the definition of measurability described above. However, if non-cystic lesions are present in the same participant, these are preferred for selection as target lesions.

Target lesions. All measurable lesions up to a maximum of 2 lesions per organ and 5 lesions in total, representative of all involved organs, should be identified as **target lesions** and recorded and measured at baseline. Target lesions should be selected on the basis of their size (lesions with the longest diameter), be representative of all involved organs, but in addition should be those that lend themselves to reproducible repeated measurements. It may be the case that, on occasion, the largest lesion does not lend itself to reproducible measurement in which circumstance the next largest lesion which can be measured reproducibly should be selected. A sum of the diameters (longest for non-nodal lesions, short axis for nodal lesions) for all target lesions will be calculated and reported as the baseline sum diameters. If lymph nodes are to be included in the sum, then only the short axis is added into the sum. The baseline sum diameters will be used as reference to further characterize any objective tumor regression in the measurable dimension of the disease.

Non-target lesions. All other lesions (or sites of disease) including any measurable lesions over and above the 5 target lesions should be identified as **non-target lesions** and should also be recorded at baseline. Measurements of these lesions are not required, but the presence, absence, or in rare cases unequivocal progression of each should be noted throughout follow up.

11.1.3 Methods for Evaluation of Disease

All measurements should be taken and recorded in metric notation using a ruler, calipers, or a digital measurement tool. All baseline evaluations should be performed as closely as possible to the beginning of treatment and never more than 4 weeks before the beginning of the treatment.

The same method of assessment and the same technique should be used to characterize each identified and reported lesion at baseline and during follow-up. Imaging-based evaluation is preferred to evaluation by clinical examination unless the lesion(s) being followed cannot be imaged but are assessable by clinical exam.

Clinical lesions. Clinical lesions will only be considered measurable when they are superficial (*e.g.*, skin nodules and palpable lymph nodes) and ≥ 10 mm in diameter as assessed using calipers (*e.g.*, skin nodules). In the case of skin lesions, documentation by color photography, including a ruler to estimate the size of the lesion, is recommended.

Chest x-ray. Lesions on chest x-ray are acceptable as measurable lesions when they are clearly defined and surrounded by aerated lung; however, CT is preferable.

Conventional CT and MRI. This guideline has defined measurability of lesions on CT scan based on the assumption that CT thickness is 5mm or less. If CT scans have slice thickness greater than 5 mm, the minimum size of a measurable lesion should be twice the slice thickness. MRI is also acceptable in certain situations (*e.g.* for body scans).

Use of MRI remains a complex issue. MRI has excellent contrast, spatial, and temporal resolution; however, there are many image acquisition variables involved in MRI, which greatly impact image quality, lesion conspicuity, and measurement. Furthermore, the availability of MRI is variable globally. As with CT, if an MRI is performed, the technical specifications of the scanning sequences used should be optimized for the evaluation of the type and site of disease. Furthermore, as with CT, the modality used at follow-up should be the same as was used at baseline and the lesions should be measured/assessed on the same pulse sequence. It is beyond the scope of the RECIST guidelines to prescribe specific MRI pulse sequence parameters for all scanners, body parts, and diseases. Ideally, the same type of scanner should be used and the image acquisition protocol should be followed as closely as possible to prior scans. Body scans should be performed with breath-hold scanning techniques, if possible.

FDG-PET. While FDG-PET response assessments need additional study, it is sometimes reasonable to incorporate the use of FDG-PET scanning to complement CT scanning in assessment of progression (particularly possible 'new' disease). New lesions on the basis of FDG-PET imaging can be identified according to the following algorithm:

- (a) Negative FDG-PET at baseline, with a positive FDG-PET at follow-up is a sign of PD based on a new lesion.
- (b) No FDG-PET at baseline and a positive FDG-PET at follow-up: If the positive FDG-PET at follow-up corresponds to a new site of disease confirmed by CT, this is PD. If the positive FDG-PET at follow-up is not confirmed as a new site of disease on CT, additional follow-up CT scans are needed to determine if there is truly progression occurring at that site (if so, the date of PD will be the date of the initial abnormal FDG-PET scan). If the positive FDG-PET at follow-up corresponds to a pre-existing site of disease on CT that is not progressing on the basis of the anatomic images, this is not PD.
- (c) FDG-PET may be used to upgrade a response to a CR in a manner similar to a

biopsy in cases where a residual radiographic abnormality is thought to represent fibrosis or scarring. The use of FDG-PET in this circumstance should be prospectively described in the protocol and supported by disease-specific medical literature for the indication. However, it must be acknowledged that both approaches may lead to false positive CR due to limitations of FDG-PET and biopsy resolution/sensitivity.

Note: A 'positive' FDG-PET scan lesion means one which is FDG avid with an uptake greater than twice that of the surrounding tissue on the attenuation corrected image.

PET-CT. At present, the low dose or attenuation correction CT portion of a combined PET-CT is not always of optimal diagnostic CT quality for use with RECIST measurements. However, if the site can document that the CT performed as part of a PET-CT is of identical diagnostic quality to a diagnostic CT (with IV and oral contrast), then the CT portion of the PET-CT can be used for RECIST measurements and can be used interchangeably with conventional CT in accurately measuring cancer lesions over time. Note, however, that the PET portion of the CT introduces additional data which may bias an investigator if it is not routinely or serially performed.

MIBG (meta-iodobenzylguanidine). The following is recommended, to assure high quality images are obtained.

Patient preparation: Iodides, usually SSKI (saturated solution of potassium iodide), are administered to reduce thyroidal accumulation of free radioiodine, preferably beginning the day prior to injection and continuing for 3 additional days (4 days total). For infants and children, one drop t.i.d. is sufficient, for adolescents 2 drops t.i.d., and for adults 3 drops t.i.d. Participants and/or parents are asked about exposure to potential interfering agents. If none is noted, an indwelling intravenous line is established. The dose of MIBG is administered by slow intravenous injection over 90 seconds.

Images from the head to the distal lower extremities should be obtained.

I-123MIBG scintigraphy is performed to obtain both planar and tomographic images.

Planar: Anterior and posterior views from the top of the head to the proximal lower extremities are obtained for 10 minutes at 24 hours and occasionally at 48 hours following injection of 10 mCi/1.7 square meters of body surface area (~150 μ Ci/kg, maximum 10 mCi). Anterior views of the distal lower extremities are adequate. A large field of view dual head gamma camera with low energy collimators is preferred.

SPECT: Most participants receiving I-123 MIBG also undergo SPECT at 24 hours, using a single or multi-headed camera with a low energy collimator. The camera is rotated through 360 degrees, 120 projections at 25 seconds per stop. Data are reconstructed using filtered back projections with a Butterworth filter and a cut off

frequency of 0.2-0.5. SPECT/CT may be performed at institutions with this capacity.

Ultrasound. Ultrasound is not useful in assessment of lesion size and should not be used as a method of measurement. Ultrasound examinations cannot be reproduced in their entirety for independent review at a later date and, because they are operator dependent, it cannot be guaranteed that the same technique and measurements will be taken from one assessment to the next. If new lesions are identified by ultrasound in the course of the study, confirmation by CT or MRI is advised. If there is concern about radiation exposure from CT, MRI may be used instead of CT in selected instances.

Endoscopy, Laparoscopy. The utilization of these techniques for objective tumor evaluation is not advised. However, such techniques may be useful to confirm complete pathological response when biopsies are obtained or to determine relapse in trials where recurrence following complete response (CR) or surgical resection is an endpoint.

Tumor markers. Tumor markers alone cannot be used to assess response. If markers are initially above the upper normal limit, they must normalize for a participant to be considered in complete clinical response. Specific guidelines for both CA-125 response (in recurrent ovarian cancer) and PSA response (in recurrent prostate cancer) have been published [*JNCI* 96:487-488, 2004; *J Clin Oncol* 17, 3461-3467, 1999; *J Clin Oncol* 26:1148-1159, 2008]. In addition, the Gynecologic Cancer Intergroup has developed CA-125 progression criteria which are to be integrated with objective tumor assessment for use in first-line trials in ovarian cancer [*JNCI* 92:1534-1535, 2000].

Cytology, Histology. These techniques can be used to differentiate between partial responses (PR) and complete responses (CR) in rare cases (e.g., residual lesions in tumor types, such as germ cell tumors, where known residual benign tumors can remain).

The cytological confirmation of the neoplastic origin of any effusion that appears or worsens during treatment when the measurable tumor has met criteria for response or stable disease is mandatory to differentiate between response or stable disease (an effusion may be a side effect of the treatment) and progressive disease.

